1.5 MODIFICATIONS TO THE STATISTICAL SECTION OF THE PROTOCOL

This section summarizes major changes to the protocol statistical section with emphasis on changes after study start (after the first patient was enrolled) but before the study is unblinded.

The protocol history table below gives the timing, rationale, and key details of major changes to the protocol statistical section.

Table 1 - Protocol amendment statistical changes

Amendment Number	Date Approved	Rationale	Description of statistical changes
2	31-May-2018		
The following text:
 
The sample size of this study was based on a comparison between dupilumab versus placebo with regard to the primary endpoints of annualized rate of severe exacerbations at Week 52. Assuming the number of severe exacerbations follows a negative binomial distribution with a dispersion parameter of 1.5, a placebo annualized rate of exacerbations being 1.0, a randomization ratio of 2:1, with 294 randomized patients (196 for dupilumab and 98 for matching placebo group), the study will have approximately 90% power to detect a 50% relative risk reduction (ie, annualized rate of 0.5 for the dupilumab group) in the annualized rate of severe exacerbations at the 2-tailed significance level of $\alpha=0.05$. This calculation assumes a linear discontinuation rate (20% at 1 year), thus the average exposure duration for patients is 0.9 year.
 
Was replaced with:
 
The sample size of this study was based on a comparison between dupilumab versus placebo with regard to the primary endpoints of annualized rate of severe exacerbations at Week 52. [REDACTED]
 
[REDACTED]
 
[REDACTED]
 
[REDACTED]
 
[REDACTED]
 
[REDACTED]
 
[REDACTED]
 
[REDACTED]
 
[REDACTED]
 
[REDACTED]
 
[REDACTED] This calculation also assumes a linear discontinuation rate (20% at 1 year), thus the average exposure duration for patients is 0.9 year.

3	18-October-2019		
The following text was added:
 
The sample size of this study was based on a comparison between dupilumab versus placebo with regard to the primary endpoints of annualized rate of severe exacerbations at Week 52. [REDACTED]
 
[REDACTED]
 
[REDACTED]
 
[REDACTED]

Amendment Number	Date Approved	Rationale	Description of statistical changes

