2.4.4.1 Analysis of primary efficacy endpoint(s)

Primary statistical model and adjustment for covariates

The primary analysis of the annualized rate of severe exacerbation events during the 52-week placebo-controlled treatment period is to assess the efficacy of dupilumab. In this primary approach, for the patients who prematurely discontinue treatment, their off-treatment measurements up to Week 52 or the study withdrawal whichever comes earlier will be included for the analysis. Patients who permanently discontinue the study medication will be asked and encouraged to return to the clinic for all remaining study visits. If a patient stays in study until the end of the 52-week treatment period, all severe exacerbation events that happen up to Visit 28 will be included in the primary analysis, regardless whether the patient is on-treatment or not, and the observation duration is defined as from randomization to Visit 28. If a patient withdraws from the study prior to the end of the 52-week treatment period, all observed severe exacerbation events up to the last contact date will be included in the analysis, and the observation duration is defined as from randomization to the last contact date. No imputation will be performed for the unobserved events that may happen after study discontinuation and up to Week 52. This estimand compares

the rate of severe exacerbation for the patients randomized to the dupilumab and placebo arms, regardless of what treatment patients actually received. It assesses the benefits of the treatment policy or strategy relative to placebo.

The annualized rate of severe exacerbation events as defined in [Section 2.1.3.1](#) will be analyzed using a negative binomial regression model. The analysis for the annualized severe exacerbation rate will be performed in the Type 2 inflammatory asthma phenotype, baseline blood eosinophils ≥ 0.3 Giga/L, baseline blood eosinophils ≥ 0.15 Giga/L, baseline FeNO ≥ 20 ppb and full ITT populations.

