When performing the analysis for the annualized severe exacerbation rate in the Type 2 inflammatory asthma phenotype, baseline blood eosinophils ≥ 0.15 Giga/L or full ITT population, the model will include the total number of events that occur during the observation period defined above as the response variable, with the treatment arm, age, baseline weight (≤ 30 kg, >30 kg), region, baseline eosinophil level (<0.3 Giga/L, ≥ 0.3 Giga/L), baseline FeNO level (<20 ppb, ≥ 20 ppb), baseline ICS dose level (medium/high) and number of severe exacerbation events within 1 year prior to the study as covariates. When performing the primary endpoint analysis in the baseline blood eosinophils ≥ 0.3 Giga/L population, the baseline eosinophil level will be removed from the model covariates. When performing the primary endpoint analysis in the baseline FeNO ≥ 20 ppb population, the baseline FeNO level will be removed from the model covariates.

Treatment groups, baseline weight, region, baseline eosinophil level, baseline FeNO level, and baseline ICS dose level will be treated as categorical variables. Age and number of severe exacerbation events within 1 year prior to the study will be treated as continuous variables. Log transformed observation duration will be the offset variable. In the case where the negative binomial regression model may not converge, a categorical variable for the number of severe exacerbation events within 1 year prior to study (1, 2, more than 2) will replace the corresponding continuous variable in the model. A similar approach will also be applied to other analyses for severe exacerbation endpoint if applicable.

Comparisons of the annualized event rates between dupilumab and placebo will be derived by testing dupilumab group versus placebo. The estimated annualized event rate for each treatment group and its two-sided 95% confidence intervals will be derived from the negative binomial model.

Sample SAS code can be found below:

```
proc glimmix data=event;
  class weight eosblgpn1 fenoblgrn ics trt01pn cntygr1n;
  model numevents=trt01pn age weight eosblgpn1 fenoblgrn ics cntygr1n asmanum
    /offset=logdur dist=negbin link=log solution;
run;
```

If the model fails to achieve convergence, different estimation algorithms will be applied following the order: default→LAPLACE→QUAD; if the non-convergence issue still exists, other handling may be considered. The adjustment will be added to the footnote of the corresponding outputs.

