For each patient with partial missing data of severe exacerbation events, the unobserved number of events after study discontinuation up to Week 52 will be imputed on monthly basis. Since the definition of severe exacerbation in [Section 2.1.3.1](#) requires the start dates of 2 consecutive severe exacerbation events experienced by one patient to depart at least 28 days from each other, each patient is possible to have a maximum of one event per month that is defined as 28 days. A logistic regression model therefore can be used to impute whether a patient has an event or not for each of the corresponding unobservable months. This imputation will be repeated multiple times. A final statistical inference will be obtained by using Rubins' formula to combine the binomial regression results based on each of the imputed datasets. Details of the PMM model are described in [Appendix D](#).

- *Control-based PMM*

Similar to aforementioned PMM model except that the individual monthly mean probability will be calculated based on observations in placebo arm only in the logistic regression, with adjustment of missing observation duration.

- *Tipping point analysis*

Similar to aforementioned PMM model except that if a patient with missing data is on dupilumab, the odds in the logistic model for each unobservable month will be increased, and vice versa if the patient is on placebo, the odds will be decreased. This adjustment will artificially lower the predicted event rates in placebo group and increase the predicted event rates in Dupilumab group. For each increasing/decreasing ratio, a p-value can be obtained based on the imputed dataset with this specific ratio. A sequence of different ratios will be explored until p-value becomes >0.05 .

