The missing data sensitivity analyses for the primary endpoint analysis will be performed in the Type 2 inflammatory asthma phenotype and baseline blood eosinophils ≥ 0.3 Giga/L populations. For each of the above methods, a negative binomial model will be fitted using the complete dataset composed of observed and imputed data, including the total number of observed and imputed events during the 52 weeks as the response variable. When performing the sensitivity analyses in the population with Type 2 inflammatory asthma phenotype, the model will include the treatment group, age, baseline weight (≤ 30 kg, >30 kg), region (pooled country), baseline eosinophil level, baseline FeNO level, baseline ICS dose level and number of severe exacerbation events within 1 year prior to the study as covariates. When performing the sensitivity analyses in the population with baseline blood eosinophils ≥ 0.3 Giga/L, the baseline eosinophil level will be removed from the model covariates. Log transformed observation duration will be the offset variable.

More details of the imputation and analyses methods are provided in [Appendix D](#).

Sensitivity analysis related to COVID-19 Pandemic

To assess missing data due to COVID-19 pandemic, missing data from patients who were discontinued from the study before Week 52 due to COVID-19 will be imputed using a manner similar to pattern mixture model as mentioned above except breaking down the 'Other' discontinuation reason into 'Due to COVID-19 or not' when defining the missing patterns.

Subgroup analyses

To assess the consistency of treatment effects across the subgroup levels, subgroup analyses will be performed for the annualized rate of severe exacerbation event during the 52-week treatment period by:

- Gender (Male, Female)
- Region (Latin America, Eastern Europe, and Western Countries)
- Race (Caucasian/White, Black/of African descent, Asian/Oriental, all the other)
- Background ICS dose levels at randomization (medium, high)

- Baseline blood eosinophil level (<0.3 Giga/L, ≥ 0.3 Giga/L; <0.15 Giga/L, ≥ 0.15 Giga/L; <0.15 Giga/L, ≥ 0.15 - <0.3 Giga/L, ≥ 0.3 - <0.5 cells/ μ L, ≥ 0.5 cells/ μ L)
- Baseline FeNO level (<20 ppb, ≥ 20 - <35 ppb, ≥ 35 ppb)
- Eos-FeNO Quadrant (0.15-20) 1 (H-H): Baseline blood eosinophil level ≥ 0.15 Giga/L and Baseline FeNO ≥ 20 ppb
- Eos-FeNO Quadrant (0.15-20) 2 (H-L): Baseline blood eosinophil level ≥ 0.15 Giga/L and Baseline FeNO <20 ppb

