Appendix D Handling of missing data

Annualized severe exacerbation events during the 52-Week period

- ***Pattern mixture model (PMM)***

Step 1. The 52-week observation period is partitioned into monthly (4-week) segments. In the analysis, for each patient, in each month, an imputation flag (impute_{fl}) will indicate whether the patient needs imputation in that month.

Step 2. *Calculation of observed monthly mean of event count*

Within each month, the logistic regression model will be fitted to the observed data to model coefficient estimates and the estimated variance-covariance matrix, with adjusting for the planned treatment group, age, baseline weight (≤ 30 kg, > 30 kg), region (pooled country), baseline eosinophil level (removed for the baseline eosinophils ≥ 0.3 Giga/L population), baseline FeNO level, baseline ICS dose level, and number of severe exacerbation events within 1 year prior to the study. From the posterior distribution of the model coefficients, we randomly draw 40 sets of iid samples. As a result, for each patient and in each month, 40 estimated probabilities can be obtained by using the 40 samples of coefficients and the patient's covariates values.

Step 3. *Imputation of event count after study withdrawal*

If a patient withdraws from the study at the k th ($1 \leq k < 28$) day of Month i prior to Week 52, and experienced a severe exacerbation within the first k days, this patient will be considered as “observed” (impute_{fl}=0) up to Month i and will need imputations (impute_{fl}=1) from Month $i+1$ to Month 13 (Week 52).

If a patient withdraws from the study at the k th ($1 \leq k < 28$) day of Month i prior to Week 52, and has no severe exacerbation in Month i , this patient will be considered as “observed” (impute_{fl}=0) up to Month $i-1$ and will need imputations (impute_{fl}=1) from Month i to Month 13 (Week 52).

For a patient who needs imputation from Month $i+1$ to Month 13, in each month, 40 independent random samples will be respectively drawn from 40 estimated Bernoulli distributions, whose probabilities are obtained in Step 2. For each patient who early withdraws from the study, 40 sets of complete event count data can be obtained by summing the observed event count prior to withdrawal and each series of imputed binary events after withdrawal up to Week 52.

Step 2 and 3 can be realized by using PROC MI in SAS. Sample code can be found below:

```
proc mi data=dd seed=9816388 nimpute=40 out=outdata;  
by month;  

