class outcome trt01pn weight eosbgp1n cntygr1 icsgrp fenoblgrn ;  
monotone reg (asmanum/details)  
logistic (outcome=trt01pn age weight eosbgp1n cntygr1 icsgrp fenoblgrn asmanum/details  
DESCENDING);  
var eosbgp1n cntygr1 age icsgrp trt01pn fenoblgrn asmanum outcome;  
run;
```

Step 4. A negative binomial model with the same set of covariates as in the primary endpoint analysis will be fitted with 40 sets of complete datasets obtained in Step 3, so as to obtain 40 sets of treatment effect estimates and p-values accordingly. Log transformed observation duration will be the offset variable for patients who complete the 52-Week treatment/study period, and log transformed 52 weeks will be the offset variable for patients who discontinue the study before Visit 18 (Week 52). At last, the SAS MIANALYZE procedure will be used to generate statistical inferences by combining results from the 40 analyses using Rubin's formula.

Step 4 can be realized by using PROC MIANALYZE in SAS. Sample code can be found below

```
proc mianalyze data=rr_conv;  
by Label;  
modeleffects Estimate;  
stderr StdErr;  
ods output ParameterEstimates=rr_pooled;  
run;  
proc mianalyze data=aer_conv;  
by TRT01PN;  
modeleffects Estimate;  
stderr;  
ods output ParameterEstimates=aer_pooled;  
run;
```

- **Control-based PMM**

All steps are the same as the aforementioned approach except in **Step 2**: the individual monthly mean probability will be calculated based on observations in placebo arm only, with adjustment of missing observation duration.

- **Tipping point analysis**

The tipping point analysis for severe exacerbation events will use the similar approach as PMM-MI with tipping values for the odds

Step 1. Estimation for the monthly binary event probability using observed data

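### The control-based check on the exacerbation rate fits a placebo-only logistic model in every 28-day month; at the superseded planning values it over-imputes events about two- to four-fold and can make a robust result look fragile

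*SAP*

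**What the plan says.** SAP section 2.4.4.1 plans three missing-data checks on the primary endpoint: a pattern mixture model (PMM), a control-based PMM and a tipping-point analysis. On where they are run: "The missing data sensitivity analyses for the primary endpoint analysis will be performed in the Type 2 inflammatory asthma phenotype and baseline blood eosinophils" ≥0.3 Giga/L populations.

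Appendix D gives the mechanics of the PMM:

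- **Step 2:** "Within each month, the logistic regression model will be fitted to the observed data to model coefficient estimates and the estimated variance-covariance matrix". The adjusters are treatment, age, weight group, region, eosinophil level (dropped in the ≥0.3 population), FeNO level, ICS dose level and number of prior exacerbations. Forty coefficient sets are drawn from each fit. The sample PROC MI code runs by month.
- **Step 3:** "40 independent random samples will be respectively drawn from 40 estimated Bernoulli distributions, whose probabilities are obtained in Step 2".

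The control-based version keeps every step and changes only the data behind Step 2: "the individual monthly mean probability will be calculated based on observations in placebo arm only, with adjustment of missing observation duration". Section 2.4.4.1 describes it the same way: "based on observations in placebo arm only in the logistic regression, with adjustment of missing observation duration". Neither document defines the duration adjustment.

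The only convergence provisions are in section 2.4.4.1 and are written for the negative binomial model: recode prior events into three classes, change the estimation algorithm, then consider other handling. On the recoding, the SAP adds: "A similar approach will also be applied to other analyses for severe exacerbation endpoint if applicable".

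**The concern.** Dropping the dupilumab arm removes about two thirds of the patients from a model that is already split into 13 monthly pieces. The covariate list loses only the treatment term. With fewer events than coefficients in a month, maximum likelihood estimates separate or have very large standard errors.

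Drawing coefficients from such a fit is not neutral. The true monthly probability is small, so wide scatter on the logit scale pulls the average probability upward. These inflated probabilities are imputed in both arms, which pulls the rate ratio towards 1.

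A control-based analysis is meant to attenuate the effect to some extent. Extra attenuation caused by the fitting method cannot be told apart from it in the output. A reader could take a numerical artefact as evidence that the primary result depends on missing data.

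**Working it through.** **Inputs**

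- Population sizes: about 345 (Type 2) and 255 (eosinophils ≥0.3 Giga/L), SAP 1.1. At 2:1, about 115 and 85 are on placebo.
- Withdrawal: linear, 20% at one year, mean exposure 0.9 year, SAP 1.3.
- Rate and dispersion: current values are redacted. The only visible ones, in SAP 1.5, are superseded: "a dispersion parameter of 1.5, a placebo annualized rate of exacerbations being 1.0, a randomization ratio of 2:1". Rates of 0.6 and 1.5 per year are added as assumptions to show the range.

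**The visible planning figure reproduces.** With 98 and 196 patients, rates 1.0 and 0.5, dispersion 1.5 and exposure 0.9 year:

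Var(log RR) = (1/0.9 + 1.5)/98 + (1/0.45 + 1.5)/196 = 0.0456, so SE = 0.2136.

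ln 2 / 0.2136 − 1.96 = 1.285, which is 90.1% power. The SAP states approximately 90%.

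**Coefficients per monthly placebo fit.** Intercept 1, age 1, weight 1, region 2, FeNO 1, ICS 1, prior events 1 = 8. Type 2 adds eosinophil level, giving 9.

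**Events per monthly placebo fit at rate 1.0.** The probability of an event in 28 days is 1 − (1 + 1.5 × 28/365.25)^(−1/1.5) = 0.070.

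- Eosinophils ≥0.3, 20% withdrawal: 85 × 0.9 × 0.070 ≈ 5.4 events, or 0.67 per coefficient.
- Type 2, 5% withdrawal: 115 × 0.975 × 0.070 ≈ 7.8 events, or about 0.87 per coefficient.

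**Why draws inflate (illustration).** logit(0.070) = −2.59. If the drawn linear predictor has SD 1, the mean probability is 0.098 (1.4-fold). With SD 2 it is 0.165 (2.4-fold), and with SD 10 about 0.40 (5.7-fold).

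**Simulation of the written procedure.** 500 trials per setting; gamma frailty variance 1.5; true rate ratio 0.5; non-informative withdrawal spread evenly over 52 weeks; the SAP partial-month rule; 40 imputations; covariate-adjusted negative binomial model; Rubin combination. The SAP gives no rule for separated fits, so by-month fits were stopped at 8 iterations or run to 25.

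Imputed / true placebo probability:

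| Placebo rate | By month, 8 iterations | By month, 25 iterations | One pooled model | Problem months |
|---|---|---|---|---|
| 0.6 | 3.7–4.8 | 6.0–7.7 | 1.14–1.17 | 66–79% |
| 1.0 | 2.0–2.7 | 2.6–3.8 | 1.08–1.11 | 36–52% |
| 1.5 | 1.5–1.8 | 1.6–2.1 | 1.06–1.10 | 15–26% |

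Significant primary results that lose significance at rate 1.0, by month versus pooled:

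| Withdrawal | Eosinophils ≥0.3 (N=255) | Type 2 (N=345) |
|---|---|---|
| 20% | 26–34% vs 9% | 12–18% vs 5–6% |
| 10% | 8–12% vs 3% | 6–8% vs 3% |
| 5% | 6–10% vs 2% | 3–4% vs 1.5% |

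Monte Carlo error is about 1 to 3 points. At 20% withdrawal the loss is 37–66% versus 10–16% at rate 0.6, and 5–15% versus 3–6% at rate 1.5. The control-based rate ratio at rate 1.0 and 20% withdrawal is 0.63–0.66 by month and 0.59 pooled.

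**Variations at rate 1.0**

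- An intercept-only monthly fit gives 1.02–1.11, so the excess comes from the covariate load, not from control-based imputation itself.
- Recoding prior events as in section 2.4.4.1 adds a coefficient: problem months rise to 45–65% and the ratio is 2.25–3.07.
- Scaling the withdrawal month to its unobserved days leaves the by-month ratio at 2.06–2.76.
- An augmented likelihood kept by month still gives 1.9–2.2.
- Setting covariate effects to zero gives 2.2–2.6 (8 iterations) and 2.8–3.6 (25 iterations).

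**The case against.** **The coefficient draws may not carry over.** They sit in Step 2, the step the control-based version replaces, and the replacement speaks of a mean probability. Without draws the inflation at rate 1.0 is only 1.07- to 1.26-fold. The wording leaves some room for this. But Step 3 is kept and needs 40 estimated distributions with probabilities from Step 2, and section 2.4.4.1 places the placebo restriction inside the logistic regression. The reading with draws is the natural one.

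**The rates are not the trial's.** True, so the two- to four-fold figure is conditional. The direction holds at all three rates examined and worsens as the rate falls.

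**The factor applies only to imputed months.** True: at 20% withdrawal these are about a tenth of follow-up, and most significant results survive. Actual withdrawal may be lower, because for patients who stop treatment "their off-treatment measurements up to Week 52 or the study withdrawal whichever comes earlier will be included for the analysis". At 5% withdrawal in Type 2 the gap is within simulation error.

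**Programmers would notice, and other handling is allowed.** That clause is written for the negative binomial model. Choosing a new imputation model once the data show the problem is what pre-specification is meant to avoid.

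**It is a sensitivity analysis, biased against the drug.** This stands in full and limits the severity. It cannot create a false efficacy claim.

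**Conclusion.** The concern holds. As written, the control-based check fits 8 or 9 coefficients to fewer events than coefficients in each month, at placebo rate 1.0 and dispersion 1.5. It then imputes about 2.0 to 3.8 times the true placebo probability. At 20% withdrawal this raises the share of significant primary results that appear non-robust from 9% to 26–34% in the eosinophils ≥0.3 Giga/L population, and from 5–6% to 12–18% in Type 2.

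The size rests on superseded rates, non-informative withdrawal, assumed covariate distributions, coefficient draws being intended, and an unstated rule for separated fits. The primary analysis and the testing hierarchy are unaffected.

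The two-arm PMM also over-imputes (roughly 1.4- to 2-fold at rate 1.0). Its rate ratio moves by at most 0.01 at rates 1.0 and 1.5, so its conclusion is little affected there. At rate 0.6 with 20% withdrawal, 3–9% of significant results lose significance in it.

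This should be fixed before the analysis is run; it does not threaten the trial's main conclusion.

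**What to change.** Replace the control-based Step 2 in Appendix D with:

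> One logistic regression is fitted to all observed placebo patient-months, with month (1 to 13) as a linear term, the baseline covariates of PMM Step 2 without treatment, and a patient-clustered variance. Forty coefficient sets are drawn from it and give the monthly probability for every patient-month to be imputed, in both arms. In the withdrawal month, with k days observed, p is replaced by 1 − (1 − p)^((28 − k)/28).

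The last sentence is a proposed definition of the duration adjustment; if the sponsor meant something else, it should be stated. Make the matching change in section 2.4.4.1 and supply code for this analysis in place of the by-month example.

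In the eosinophils ≥0.3 population at 20% withdrawal, the pooled model has about 13 × 5.4 ≈ 69 placebo events for 9 coefficients at rate 1.0, and 43 at rate 0.6. None of 300 such fits separated.

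Using the pooled form, with treatment retained, for the PMM and tipping-point analyses too is optional but cleaner: the three checks would then differ only in their missing-data assumption.

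The cost is one appendix step, one sentence and sample code. The downside is that covariate effects are assumed constant over the 13 months.
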